5.3.2 Pregnancy

At each follow-up visit, the research nurse or study physician queries all female subjects with childbearing potential whether there is any change to their menstrual cycle or their birth control. Urine pregnancy tests will be performed as needed at the discretion of the research team. If a urine pregnancy test result is positive, a stat serum pregnancy test (human chorionic gonadotropin, HCG) shall be performed to verify pregnancy. If pregnancy is verified, therapy must be immediately discontinued and the study termination protocol followed. Please contact the Sponsor within one working day to report a pregnancy.

5.4 Treatment Group (AspireAssist plus Lifestyle Therapy)

Those subject randomized to the treatment group will undergo endoscopic A-Tube placement, Aspiration Therapy training and treatment, along with Lifestyle Therapy. The schedule of assessments for the treatment group is detailed in **Table 1-2** and described below.

A-Tube placement must occur within 30 days of the screening visit. Subjects who do not meet this timeline will be withdrawn from the study.

5.4.1 A-TubeTM Insertion Procedure Visit

Prior to A-Tube insertion, the study coordinator shall notify the Aspire study liaison of the date of the procedure and verify that all enrollment criteria have been met. The subject must have signed and dated the consent form, met all inclusion criteria, met none of the exclusion criteria, and completed all screening and baseline procedures prior to A-Tube placement.

The subject shall be instructed to fast after midnight the night before the procedure and make arrangements to have someone drive him/her home after the procedure.

Data collected at the time of A-Tube insertion shall include:

- Body weight (using the designated study scale)
- Unidentifiable photograph of the subject taken prior to A-Tube placement (one front and one side view without the subject's head appearing in the photo); to be used by the Sponsor in scientific presentations or publications. (An additional photo will be taken at 52-weeks.)
- Any changes in health since the screening visit (these will be considered "preexisting")
- Any changes to medications (these will be considered "preexisting")

Detailed instructions for the AspireAssist A-Tube placement and use are in **Appendix D**.

An A-Tube is placed in subjects by a gastroenterologist or endoscopicallytrained surgeon in an endoscopy suite. This procedure involves performing upper gastrointestinal endoscopy and close medical monitoring. The choice of specific sedative and a decision whether an anesthesiologist or anesthetist should be present during the procedure is left to the discretion of the endoscopist, based on the subject's risk of apnea and other complications. A history of disordered breathing, obstructive sleep apnea, obesityhypoventilation syndrome, and thick neck with restricted movement are important risk factors that suggest use of short acting sedation and more careful monitoring under the supervision of an anesthesiologist or anesthetist should be considered. Pulse oximetry and heart rate are monitored throughout the procedure. A routine upper endoscopy, which includes examination of the esophagus, stomach and the proximal duodenum, is performed. The tip of the endoscope is then positioned in the gastric body or antrum of the stomach, and the A-Tube exit site is prepped and draped in sterile fashion. The site for A-Tube placement should be identified by both transillumination and finger indentation. The skin and subcutaneous tissue at the exit site area is injected with an anesthetic, and a small (<1-cm) horizontal skin incision is made by using a scalpel. The safe tract technique (no air bubbles observed after inserting a needle with syringe containing several ml of saline or anesthetic until the needle is visualized in the gastric lumen) should be used to ensure no intervening loop of bowel is present between the stomach and the anterior abdominal wall. A metal stylet with a plastic sheath is passed through the abdominal wall into the gastric lumen. After removing the inner stylet, a wire is passed through the plastic sheath into the stomach lumen. The wire is grasped with a snare, and both the endoscope and wire are removed through the mouth. The A-Tube delivery system is attached to the oral portion of the wire and pulled through the abdominal wall exit site.

The endoscope is passed into the stomach again to confirm proper placement of the tube and internal bumper. Endoscopic photographic imaging will be performed at the end of the procedure to document proper A-Tube placement.

After endoscopic A-Tube placement is completed, subjects are observed in the recovery area of the endoscopy suite or admitted to the hospital for up to 24 h, at the discretion of the physician performing the procedure.

Antibiotic prophylaxis for 24 hours is given to each subject: 1 g of cefazolin sodium intravenously approximately 30-60 minutes before A-Tube placement and subsequent oral cephalexin (500 mg q 12 hrs) for 24 hours (two doses) after endoscopy. If the subject is allergic to cefazolin, either clindamycin (900 mg intravenously) can be given followed by oral clindamycin therapy (300 mg p.o. every 8 hours) for 24 hours (three doses) after endoscopy or vancomycin (1 gram intravenously) can be given before the procedure (no post endoscopy therapy. Ultimately, the exact antibiotic regimen used in any subject is at the discretion of the study site gastroenterologist.

If the A-Tube cannot be placed safely, based on the judgment of the endoscopist, or if an exclusion criteria is discovered during endoscopy, the procedure should be terminated and subject discharged from further participation in the study.

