The incidence of procedure-related, device-related, and therapy-related adverse events will be measured, as well as the incidence of device related, or unrelated, serious adverse events, including unanticipated adverse device effects. Also, the development of adverse eating behaviors will be assessed.

Schedule of Assessments:

The Schedule of Assessments for the Control Group and the AT group are shown in **Tables 1-3**.

Table 1: Schedule of Assessments, Year 1-AT Group

YEAR 1	Screen	lom		Da	ay		Week of Therapy															
Visit	Screen	Random	0	1	7	14	0	0.5**	2	6	10	14	20	24	28	32	36	40	44	48	52	Total
Visit window (+ days)			0	0	1	4	2	1	2	7	7	7	7	7	7	7	7	7	7	7	7	
Informed consent	Х																					1
Screening interview	Х																					1
Medical History & Physical Exam	х																				х	2
EKG	х																				х	2
IWQOL	х																				х	2
Questionnaire on Eating and Weight Patterns (QEWP)	х											х			Х						х	4
Eating Disorders Examination (EDE)	х											х			х						х	4
Randomization phone call		х																				1
A-Tube placement			х																			1
Skin-Port placement, Aspiration training, Initiate treatment						х																1
Phone check (RC or RN)				х			х															2
MD visit					х							х			х						х	4
Medical & Study Visit (weight, vital signs, concom meds, med																						16
adherence, AE's)					Х	х		X	Х	Х	Х	х	х	х	Х	Х	Х	Х	х	Х	Х	16
Initial body weights	х		x*																			2
Dietary Evaluation					х																	1
Lifestyle Therapy						х			х	х	х	х	х		х		х		х		х	10
Height	х																					1
Urine pregnancy	х																					1
Urine protein (dipstick)						х		х	х	х	х	х	х		х		х		х		х	11
Electrolyte panel+ magnesium + calcium								х	х	х	х	х	х				х		х			8
CMP + Magnesium	х														Х						х	3
CBC	х																				х	2
Hemoglobin & hematocrit												х			х							2
PT/PTT	х																					1
TSH	х																					1
Lipid Panel	х														х						х	3
Iron	х											х			х						х	4
Vitamin D 25-OH	х																				х	2
Hemoglobin A1C	х											х			х						х	4
DEXA	х																				х	2
Subject photograph			х																		х	2
Town Hall meetings***		•	•	•							I	Every	other	mon	th aft	er 3 A	AT gro	oup st	ıbject	s are	enroll	ed
A-Tube shortening																	reede	_				

Table 2: Schedule of Assessments, Years 2-5-AT

YEARS 2-5								Week	of Th	ierapy	7							

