4.2 Exclusion Criteria

- 1. Previous abdominal surgery that significantly increases the medical risks of gastrostomy tube placement
- 2. Esophageal stricture, pseudo-obstruction, severe gastroparesis or gastric outlet obstruction, inflammatory bowel disease
- 3. History of refractory gastric ulcers
- 4. Ulcers, bleeding lesions, or tumors discovered during endoscopic examination.
- 5. History of radiation therapy to the chest or abdomen
- 6. Uncontrolled hypertension (blood pressure >160/100).
- 7. Diabetes treated with insulin or sulfonylurea medications
- 8. Any change in diabetes medication in previous 3 months
- 9. Hemoglobin A1C >9.5%
- 10. History or evidence of serious pulmonary or cardiovascular disease, including acute coronary syndrome, heart failure requiring medications, or NYHA (New York Heart Association) class III or IV heart failure (defined below):

Class III: patients with marked limitation of activity and who are comfortable only at rest

Class IV: patients who should be at complete rest, confined to bed or chair and who have discomfort with any physical activity

- 11. Coagulation disorders (platelets < 100,000, PT > 2 seconds above control or INR > 1.5)
- 12. Anemia (Hemoglobin <11.0 g/dL in women and <12.5 g/dL in men)
- 13. Liver enzymes (ALT and AST) ≥3.0 times the upper limit of normal
- 14. Thyroid Stimulating Hormone (TSH) >1.5 x upper limit of normal at screening.
- 15. Osteoporosis (DEXA T-Score \leq -2.5 standard deviations below normal peak values).
- 16. History of fragility fractures (fractures resulting from a fall from a standing height or less, or presenting in the absence of obvious trauma)
- 17. Pregnant or lactating
- 18. Diagnosed Bulimia or diagnosed Binge Eating Disorder (using DSM IV criteria)
- 19. Night Eating Syndrome (diagnosed by EDE)
- 20. Serum potassium < 3.8 mEq/L
- 21. Chronic abdominal pain that would potentially complicate the management of the device
- 22. Taking a GLP-1 agonist < 6 months.
- 23. Taking prescription or over-the-counter medications for weight loss in the last 3 months before screening, or planning to participate in a commercial weight loss program in the next 24 months. This includes taking medications for an unrelated medical condition which have been shown to result in weight loss such as Topiramate or Bupropion.

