5.3 Control Group

Subjects randomized to the Control Group will participate in 14 Medical & Study visits and a 10-session diet and behavioral education weight loss

program called "Lifestyle Therapy" (see **Appendix C**), which will be delivered to subjects over 52 weeks. These Lifestyle Therapy sessions may be given individually during the same visit as the Medical & Study visits or in a group with other subjects who are assigned to the Control Group.

Each individual Lifestyle Therapy session will last 20-30 minutes and group sessions, about 60 minutes; the sessions will be given at week 0, 2, 6, 10, 14, 20, 28, 36, 44, and 52.

Topics include includes nutritional, physical activity, and behavioral education topics. Subjects are instructed to follow a structured eating plan, which involves eating three meals a day, eating slowly and chewing food well, drinking plenty of fluids with each meal, and limiting snacking between meals. Physical activity topics include the health benefits of physical activity and strategies for increasing lifestyle activity. The behavioral program emphasizes strategies of self-monitoring and goal-setting, and includes problem-solving, dealing with high-risk situations / cues for unhealthy eating, and stress management.

All subjects will be asked to take a multivitamin and mineral supplement daily during the lifestyle intervention program.

The Medical & Study visits occur at weeks 0, 2, 6, 10, 14, 20, 24, 28, 32, 36, 40, 44, 48, and 52, as outlined in the study assessment schedule in **Table 3**.

All Medical & Study visits will include the following assessment and procedures:

- Body weight
- Blood pressure and temperature
- Presence of normal menses in women
- Adverse Events
- Concomitant medications
- Adherence with taking study-related medications (i.e. multivitamin supplement)
- Lifestyle Therapy (only at weeks 0, 2, 6, 10, 14, 20, 28, 36, 44, and 52)

Additional procedures and assessments are performed at visits as shown in **Table 3**:

- Blood tests
- Urine (dipstick) protein test

- Physical Examination
- EKG
- Eating Disorder Examination (EDE)
- DEXA
- Questionnaires (IWQOL, QEWP-R)

If a subject develops 2+proteinuria (100mg/dL) as measured by two successive dipstick analyses, random urine shall be collected to measure protein and creatinine to calculate protein to creatinine ratio.

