5.4.2.3 Day 14 Visit: Skin-Port Placement / Aspiration Initiation & Instruction

Approximately 14 days (no sooner than 10 days) after A-Tube placement, the subject shall return to the medical center for study assessments, Skin-Port

placement, and Aspiration Therapy training and initiation. The following assessments occur:

- · Body weight
- Blood pressure and temperature
- Stoma site healing
- Adverse Events
- Changes to medications
- Lifestyle Therapy
- Urine protein (dipstick)

The device installation is not considered complete until the Skin-PortTM is fastened to the A-Tube. This procedure is explained in detail in the AspireAssist Skin-Port Instruction for Use (**Appendix F**). Briefly, the ideal length of the Skin-Port from the belly is determined, the subject lies down, the A-Tube is cut and the Skin-Port snapped in place. The length of tube removed shall be recorded. The entire procedure takes about 10 minutes to perform. Once the A-Tube is converted to a low profile Skin-Port, the subjects are trained to: 1) aspirate gastric contents after meals by using the specialized CompanionTM aspiration device 2) maintain a clean A-Tube site, and 3) recognize signs and symptoms of potential A-Tube complications (see **Appendix I**).

Aspiration Therapy starts at the time the Skin-Port is fastened to the A-Tube. Subjects are instructed to consume a structured eating plan, which involves eating three meals a day, chewing food well, drinking a minimum of 16 ounces of non-caloric fluid with each meal, a minimum of 64 ounces of non-caloric fluid per day (including fluids ingested at meals) and limit snacking between meals. Subjects are also instructed to call their study team immediately if they are experiencing severe diarrhea or vomiting at any time with Aspiration Therapy to minimize the risk of fluid imbalances.

The aspiration procedure is performed approximately 20 minutes after finishing a meal and takes approximately 10 minutes to complete. The procedure involves connecting the Companion to the Skin-Port, which results in draining a portion of ingested food from the stomach (into a waste container or toilet), thereby preventing passage of food into the small intestine where food absorption occurs. Instructions for appropriate

aspiration of gastric contents are described in the AspireAssist User's Manual (Appendix H).

5.4.3 Phone Call at Week 0

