5.5.1 Follow-Up Visits

The study entails one follow-up visit at 48-72 hours (denoted by week "0.5") after initiation of Aspiration Therapy and another 13 follow-up visits at weeks 2, 6, 10, 14, 20, 24, 28, 32, 36, 40, 44, 48, and 52 after initiation of Aspiration Therapy, as outlined in the study assessment schedule in **Table 1** and **2**. Follow-up visits starting at week 2 are to occur to within 7 days of scheduled visit window.

All follow-up visits will include the following assessment and procedures:

- Body weight
- Blood pressure and temperature
- Presence of normal menses in women
- Stoma site assessment
- Adverse Events
- Concomitant medications
- Document AspireAssist Connector counts
- Adherence with routine Aspiration Therapy
- Adherence with taking study-related medications (i.e. multivitamin and mineral supplements, as prescribed.)
- Dispense study supplies, as needed
- Skin-Port shortening, as needed

Additional procedures and assessments are performed at visits as shown in **Table 1 &2**:

- Lifestyle Therapy (at weeks 2, 6, 10, 14, 20, 28, 36, 44, and 52)
- Blood tests
- Urine (dipstick) protein test
- Physical Examination
- EKG
- Eating Disorder Examination (EDE)
- DEXA

- Questionnaires (IWQOL, QEWP-R)
- Subject Photograph

If a subject develops 2+proteinuria (100mg/dL) as measured by two successive dipstick analyses, random urine shall be collected to measure protein and creatinine to calculate protein to creatinine ratio.

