5.5.7 Pregnancy

At each follow-up visit, the research nurse or study physician queries all female subjects with childbearing potential whether there is any change to their menstrual cycle or their birth control. Urine pregnancy tests will be performed as needed at the discretion of the research team. If a urine pregnancy test result is positive, a stat serum pregnancy test (human chorionic gonadotropin, HCG) shall be performed to verify pregnancy. If pregnancy is verified, Aspiration Therapy must be immediately discontinued, the A-Tube removed, and the study termination protocol followed. Please contact the Sponsor within one working day to report a pregnancy.

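### The only mandated pregnancy test before A-Tube placement is at screening, up to 30 days earlier, and no pregnancy or menses check is listed on Day 0

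*Protocol*

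**What the plan says.** Exclusion 17 in Protocol section 4.2 reads "Pregnant or lactating". Section 5.4.1 applies the exclusions at implantation: before the tube is placed, the subject must have "met all inclusion criteria, met none of the exclusion criteria, and completed all screening and baseline procedures prior to A-Tube placement", and the coordinator must verify eligibility.

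Table 1 has a row labelled "Urine pregnancy" for the AT arm, marked at Screen only, with a row total of 1. Section 5.1 lists the same single test for women of childbearing potential. On timing, section 5.4 states that "A-Tube placement must occur within 30 days of the screening visit".

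The Day 0 list in section 5.4.1 has four items: body weight, a photograph, health changes after screening and medication changes. The lists for Day 7 (5.4.2.2) and Day 14 (5.4.2.3) also contain no pregnancy or menses item.

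Section 5.5.7 asks about menstrual cycle and birth control at follow-up visits and leaves further testing to the team's judgment. Section 5.5.1 opens its account of those visits with "The study entails one follow-up visit at 48-72 hours", counted from the start of Aspiration Therapy, which is itself "Approximately 14 days (no sooner than 10 days) after A-Tube placement".

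**The concern.** Pregnancy status can change between screening and Day 0, and a very early pregnancy may not show at screening. A rule that no exclusion may be met at placement needs a current result behind it, and the schedule supplies none later than screening. A site could follow Table 1 and section 5.4.1 to the letter and implant a woman with an unrecognised pregnancy.

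The stake is the safety of the woman and the fetus. Placement involves sedation, endoscopy and an incision through the abdominal wall. Section 7.3.1 accepts that the procedure may carry unknown risks to an embryo or fetus. Section 5.5.7 then orders a second intervention: "If pregnancy is verified, Aspiration Therapy must be immediately discontinued, the A-Tube removed, and the study termination protocol followed". Section 7.1.2 adds that removal leaves a scar and that some fistulas need endoscopic or surgical closure. A same-day test could prevent that sequence.

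**Working it through.** No power or sample-size figure is involved, and the plan states no figure of its own to reproduce. The check compares what is required before implantation with what the schedule provides, and then adds up the stated time windows.

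**Mandated checks in the AT arm**

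| Time point | Pregnancy test | Menses or birth-control query |
|---|---|---|
| Screening (5.1, Table 1) | Yes, one | Not listed |
| Day 0, placement (5.4.1) | None | None |
| Day 7 (5.4.2.2) | None | None |
| Day 14 (5.4.2.3) | None | None |
| Week 0.5 onwards (5.5.1, 5.5.7) | Discretionary | Yes |

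Mandated pregnancy tests after screening and up to placement: 0.

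**Comparison with the control arm.** Section 5.3 lists "Presence of normal menses in women" among the items for every Medical & Study visit, and the first of these is week 0. The arm with no procedure therefore has a menses check at its starting visit, while the arm that is implanted has none at Day 0.

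**Inputs for the timing**
- Screening to placement: at most 30 days (5.4).
- Placement to start of aspiration: nominally 14 days. The earliest is day 10 (5.4.2.3) and the latest is 14 + 4 = 18 days (Table 1 window).
- Start of aspiration to first follow-up visit: 48 to 72 hours, that is 2 to 3 days (5.5.1).

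**Age of the only required test at implantation:** up to 30 days.

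**Placement to first listed query**
- Nominal: 14 + 2 = 16 to 14 + 3 = 17 days.
- With the Day 14 window: 10 + 2 = 12 to 18 + 3 = 21 days.

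**Screening test to first listed query, placement on day 30**
- Nominal: 30 + 16 = 46 to 30 + 17 = 47 days.
- With the Day 14 window: 30 + 12 = 42 to 30 + 21 = 51 days.

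The 30-day figure bears directly on status at implantation. The longer intervals show how long a pregnancy could go unasked about once the tube is in place.

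**The case against.** The strongest reply is that the Protocol contradicts itself nowhere. Section 5.4.1 already forbids implanting a pregnant subject, the coordinator must verify eligibility first, and nothing stops a site from testing. This is correct, and the point is not that the plan permits such an implantation. But the duty to verify comes without a current result to verify against.

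Second, the Day 0 list does include a general item on health changes after screening, under which a known pregnancy or missed period would fall. That also stands. However, the item is recorded as preexisting rather than used as a stop rule, and it cannot reveal a pregnancy the subject does not know about.

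Third, inclusion criterion 5 requires agreement to use contraception from enrollment. This lowers the risk, but condoms and voluntary abstinence are accepted, it is not a check, and it does not cover a conception just before screening.

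Fourth, Appendix D (the A-Tube Instructions for Use) is not available here and could contain a pre-procedure test. This cannot be excluded. Even so, Table 1 sets the required assessments and its row total is 1, so the Protocol body and schedule require no such test.

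Fifth, it can be argued that Day 7 and Day 14 count as follow-up visits, because Table 1 marks them as Medical & Study visits. That would shorten the 12 to 21 day interval. It would leave the gap at implantation untouched, since both visits come after placement, and their own lists omit menses.

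Finally, a Day 0 test would also miss a conception in the last few days. It narrows the window of undetected pregnancy without closing it.

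**Conclusion.** The concern holds. The Protocol makes absence of pregnancy a condition at implantation but fixes its only mandated test at screening, up to 30 days earlier, with no pregnancy or menses item on Day 0. The first listed query afterwards is nominally 16 to 17 days after placement (12 to 21 with the Day 14 window).

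The conclusion rests on the Protocol body and its tables, with Appendix D unseen, and on taking follow-up visits as section 5.5.1 defines them. The documents give neither the number of women of childbearing potential nor a pregnancy rate, so no expected number of cases is claimed. There is no material effect on power. It is a change that should be made on safety grounds.

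**What to change.** For women of childbearing potential in the AT arm, add a urine pregnancy test on Day 0 to Table 1 (the row total becomes 2) and to the Day 0 list in section 5.4.1, with a negative result recorded before the procedure starts. If the result is positive, do not start the procedure, and confirm with the stat serum HCG already specified in section 5.5.7.

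The cost is one mark in the table, one line of text and an inexpensive test of a few minutes at an existing visit. It applies only to women of childbearing potential among the 117 planned AT subjects.

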7.3.1 Adverse events (AE)

The definitions of an Adverse Event and a treatment-emergent adverse event are as follows:

Adverse event (AE): any untoward, noxious, or unintended event experienced by a subject in a clinical trial of an investigational device, whether considered related to that investigational device or not. This definition also encompasses: 1) events that result from abuse of the device, 2) symptoms reported by the subject, 3) signs detected by the investigator or other competent observer, and 4) medically important deviations from normalcy in the results of ancillary investigations.

Treatment-emergent adverse event: an AE that is new in onset or aggravated in severity or frequency following placement of the investigational

device. This includes any change from baseline physical examination findings or results of diagnostic procedures (e.g., laboratory test, ECG, X-ray) that is clinically significant, i.e., requires diagnostic or therapeutic intervention beyond confirmation alone; however, such a finding shall not be recorded as a separate AE if it is intrinsic to, or results in, a clinical diagnosis that is recorded as an AE.

a. Anticipated Adverse Device Effects

The following events have been identified as possible (anticipated) adverse events that could be related to A-Tube implantation and use:

- 1) Risks of endoscopic placement of the A-Tube, as outlined in Section 7.1.1, are examples of procedure-related adverse events.
- 2) Risks related to the presence of the A-Tube, as outlined in Section 7.1.2, are examples of device-related adverse events.
- 3) Risks of Aspiration Therapy, as outlined in Section 7.1.3, are examples of therapy-related adverse events.
- 4) Behavioral Risks, as outlined in Section 7.1.4, are examples of therapy-related adverse events.
- 5) Risks related to concomitant drug therapy, as outlined in Section 7.1.5, are examples of study-related concomitant medication-related adverse events.
- 6) Risks of weight loss include gallstone formation, bone demineralization, alopecia, dehydration, changes in bowel habits, and loose skin are examples of therapy-related adverse events.

If the subject is female, the procedure may involve unforeseeable risks to an embryo or fetus should the subject become pregnant.

Anticipated adverse events that are NOT deemed serious adverse events need only be recorded on the CRF.

b. Unanticipated Adverse Device Effects

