8.4 Adverse Events

The number of subjects with at least one adverse event will be tabulated for each treatment group. Differences between the two treatment groups will be tested using Fisher's exact test. Then number of adverse events for each treatment group will also be tabulated.

The number of subjects and the number of adverse events will be tabulated by severity, anticipated, and causality.

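### AT health changes before A-Tube placement are set aside as preexisting, Control has a week-0 AE assessment with no such rule, and the AE comparison has no common start point

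*Protocol*

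**What the plan says.** **AT arm.** Section 5.4.1 lists the data to collect at A-Tube insertion. The list includes "Any changes in health since the screening visit", with a note that these count as preexisting. Placement may fall up to 30 days after screening (5.4), and randomisation falls within 14 days of screening (5.2). Table 1 marks the first Medical & Study visit, which carries the AE item, at Day 7 after placement.

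**Control arm.** Section 5.3 states: "The Medical & Study visits occur at weeks 0, 2, 6, 10, 14, 20, 24, 28, 32, 36, 40, 44, 48, and 52". Adverse events are on the list introduced by "All Medical & Study visits will include the following assessment and procedures", so they are assessed at week 0 as well. Lifestyle Therapy begins at that same visit: "the sessions will be given at week 0, 2, 6, 10, 14, 20, 28, 36, 44, and 52". Section 5.3 has no preexisting rule.

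**Definitions.** Section 7.3.1 defines an AE as "any untoward, noxious, or unintended event experienced by a subject in a clinical trial of an investigational device", related or not, and gives no start date. A treatment-emergent AE is "an AE that is new in onset or aggravated in severity or frequency following placement of the investigational" device.

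**Analysis.** Section 8.4: "The number of subjects with at least one adverse event will be tabulated for each treatment group". The groups are compared by Fisher's exact test, and the number of events is also tabulated. Neither is limited to treatment-emergent events.

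**The concern.** The exclusion in 5.4.1 runs to placement, not to randomisation. A subject randomised to AT may fall ill after randomisation and before placement, and the site is told to call that preexisting. A Control subject with the same illness before week 0 meets an AE question at week 0 and no instruction to set the illness aside.

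The treatment-emergent definition cannot restore balance, because it is anchored to device placement and Controls have none. Section 8.4 does not use it in any case.

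At stake is a small bias in the between-arm AE comparison of a trial whose objective includes demonstrating safety. Sites following 5.4.1 would build it into the AE records, where an analysis plan could not easily undo it. Section 5.4.1 also sits badly with 7.3.1, under which an untoward event in a trial subject is an AE whatever its cause.

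**Working it through.** There is no protocol figure to reproduce. The check compares the two arms' rules and then sizes the effect under assumptions.

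**Step 1: the rules side by side**

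| | AT | Control |
|---|---|---|
| Limit from screening to start | 30 days to placement (5.4) | none stated for week 0 |
| Rule for changes in that gap | preexisting (5.4.1) | none stated |
| First scheduled AE assessment | Day 7 after placement (Table 1) | week 0 (5.3, Table 3) |
| AE collection | placement to week 52 of therapy, about 2 + 52 = 54 weeks | week 0 to week 52, 52 weeks, plus any look-back |
| Medical & Study visits in year 1 | 16, plus 2 phone checks | 14, no phone checks |

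**Step 2: how much of the AT exclusion can follow randomisation.** If randomisation is on day 14 after screening, up to 30 − 14 = 16 days. If it is earlier, up to nearly 30 days.

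**Step 3: shift in the tested variable.** Inputs: 58 Controls (8.1.1). Assumptions, not in the protocol: a constant AE rate r of 0.5 to 2 per subject-year, and a Control look-back d of 7 to 30 days. A Control subject changes status in the 8.4 test only with an event in the gap and none in the following year:

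rise = exp(−r) × [1 − exp(−r × d/365)]

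| r per year | d, days | exp(−r) | 1 − exp(−rd/365) | Rise | Of 58 |
|---|---|---|---|---|---|
| 0.5 | 7 | 0.607 | 0.0095 | 0.6 points | 0.3 |
| 1 | 14 | 0.368 | 0.0376 | 1.4 points | 0.8 |
| 2 | 30 | 0.135 | 0.1516 | 2.1 points | 1.2 |

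Pairing the rates and gaps in other ways widens the range a little. The smallest rise is 0.5 points (r = 2, d = 7; 0.3 of 58) and the largest 2.9 points (r = 1, d = 30; 1.7 of 58).

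**Step 4: number of events**, which 8.4 also tabulates: 58 × r × d/365 gives 0.6, 2.2 and 9.5 extra Control events in the three scenarios of the table.

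**Step 5: effect on Fisher's test.** At r = 1, a 30-day look-back moves Control from 37 to 38 of 58.
- If 80% of AT (94 of 117) have an AE, p goes from 0.026 to 0.040.
- If 90% of AT (105 of 117) have an AE, p goes from 0.00007 to 0.0003.

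Across AT proportions of 80%, 90% and 95% and rates of 0.5, 1 and 2, no p-value crossed 0.05.

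**Step 6: the opposing difference.** At the same background rate of 1 per year, AT's two extra weeks raise its share with at least one AE from 63.2% to 64.6%. That equals the rise from a 14-day Control look-back, before any procedure-related event is counted.

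**The case against.** - **The Control look-back is inferred.** A reader might conclude that pre-treatment events are recorded as AEs in Control and so counted in one arm only. Section 5.3 lists adverse events as a week-0 item but does not say how far back the question reaches. This objection stands: such entries may occur, but the protocol does not require them.
- **Section 5.4.1 is a data-collection list and does not suspend reporting.** A reader might infer that a pre-placement SAE in AT escapes reporting. Section 7.3.1 requires SAE notification whatever the relation to treatment, and its AE definition covers AT subjects too. That stands. What remains is that 5.4.1 and 7.3.1 classify the same event differently and must be reconciled.
- **The device would not necessarily look safer than it is.** AT is observed for about two weeks longer, at more visits and after an invasive procedure, which pushes the other way. That stands.
- **The main safety outcomes are barely touched.** Device-, procedure- and therapy-related AEs (2.3) do not arise before placement, and section 7.1.2 reports that most earlier subjects had at least one stoma complication. That stands and keeps the point minor.
- **The counting window belongs in the SAP or in Appendix K, neither of which is shown.** This stands only in part. Section 5.4.1 is a classification rule for sites. If events are labelled preexisting and given no AE entry, a later analysis plan has no AE record to count.

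**Conclusion.** The point holds as a minor one. The protocol gives a preexisting rule to AT only, lets it run past randomisation, and compares all AEs between arms with no start date that applies to both. Taken alone, the rule favours AT.

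The effect on the tested proportion is about 0.6 to 2.1 percentage points in the three scenarios, roughly one Control subject at most, and up to 2.9 points if rates and gaps are paired freely. This rests on assumed AE rates, an assumed gap and an assumed Control look-back covering that gap.

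Two stronger readings are not supported. One takes the chance of any event in the gap (about 1% to 15% of Controls, or 0.6 to 9 of 58, in the three scenarios) as the bias. Most of those Controls would have an AE later in the year anyway, so that is not the shift in the variable 8.4 tests. The other says the comparison as a whole is tilted towards the device. The net direction is not established, given about 54 weeks of AE collection in AT against 52 in Control.

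**What to change.** - **Section 5.4.1:** limit the preexisting label, for changes in health, to those before randomisation, and reconcile it with the AE and SAE definitions in 7.3.1.
- **Section 8.4:** count AEs in both arms from randomisation over the same length of follow-up, and report AT events before placement as not related to device, procedure or therapy. The common end matters: a common start alone would leave AT observed longer, because its 52 weeks of therapy begin about 14 days after placement.

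The cost is about one sentence in each section and a few more unrelated AEs in the AT listing. Sample size, visit schedule and efficacy analyses do not change.
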